Protocol Title	Effects of face coverings during physical activity
IRB Number	020-353
Sample Size	100
Sponsor	BSW Foundation
Principal Investigator	[name]
Co-Investigators	[name], MS, EP CCRP; [name], PsyD; [name]
Study Coordinators	[name], MS; [name], MS; [name]; [name], BS

BACKGROUND AND SIGNIFICANCE

Phase I: Due to the coronavirus disease 2019 global pandemic (COVID-19), conversations surrounding the return to physical activity and sports are in the beginning stages. However, recommendations and guidelines for wearing face coverings during physical activity are conflicting among gyms, schools, and collegiate and professional sports.

The Centers for Disease Control and Prevention (CDC) recommends that all people over the age of 2 wear a cloth face covering in public settings, especially when social distancing measures are difficult to maintain.¹ Conversely, the World Health Organization (WHO) states that people should not wear face coverings when exercising, as masks may reduce the ability to breathe comfortably and that sweat can make the face coverings become wet more quickly which makes it difficult to breathe and promotes the growth of microorganisms.²

In accordance with Executive Order GA-29, the University Interscholastic League (UIL) of Texas requires students, staff, and visitors to wear face coverings when entering and exiting facilities and practice areas, and when not actively exercising. Schools may, for example, allow students who are actively exercising to remove face coverings as long as they maintain at least six feet of distance from other students and staff who are not wearing face coverings. However, schools must require students and staff to wear face coverings as they get into positions that allow them to maintain safe distancing.³ The NCAA has similar recommendations for collegiate athletics including universal masking when physical distancing is not possible.⁴ The National Football League (NFL) is currently investigating the use of modified face coverings and helmets, though specific regulations have yet to be unveiled.

There is no scientific evidence available on the impact of wearing a face covering on sports performance (exercise capacity) during this pandemic.⁵

Phase II: Previous research has found that more than 40% of patients with COVID showed neurologic manifestations at the outset, and more than 30% of those had impaired cognition.⁶ Impaired cognitive performance and reaction time during mask wearing could negatively impact. Thus, in order to investigate the possible relationship between cognitive performance during physical activity and COVID-19, Phase II will consist of a prospective, randomized crossover trial of 50 eligible participants. Investigators will compare VO2 max during two maximal

cardiopulmonary stress exercise tests (CPET) on a cycle ergometer, seven to ten days apart, and examine differences in cognitive performance. ECG monitoring will take place during exercise testing among individuals with history of COVID-19. Previous research regarding cognitive performance includes private studies completed between Sports Academy Cognition Lab (SACL) and GlaxoSmithKline Human Performance Lab (GSK-HPL) to investigate the relationship between cognitive performance and sports performance training. As part of this research, international-level cricket athletes completed daily cognitive performance assessments using the *SACL Cognition* application on iPad as part of their sport performance training. The results showed that performance on a simple reaction time (SRT) task was statistically significantly correlated to a variety of physiological sports performance measures, including heart rate, sleep quality, self-assessment of motivation, self-assessment of physical soreness. When SRT was higher (i.e., slower), heart rate, sleep quality, motivation, soreness, and freshness were measured/rated lower. Among professional rugby players, SRT was correlated with body weight, mood, sleep quality, training performance, and distance covered in training. When SRT was higher, body weight, mood, sleep quality, training performance, and training distance covered all tended to be lower. The correlations were relatively small but reached statistical significance over large samples and across a wide variety of physiological output measures, suggesting that the relationship between cognitive and physical performance is broad even if not deep. These results are relevant to the current research as they support the inclusion of a cognitive performance metric (e.g., SRT) when evaluating the effect of face coverings on overall sport performance.

Therefore, in order to investigate the impact of face coverings on exercise capacity, research will take place in two phases:

Phase I: Participants will be randomized and complete 2 treadmill trials including (1) cardiopulmonary exercise tests (CPET) with face covering, and (2) CPET without face covering.

Phase II: Participants will be randomized and will complete 2 cycle ergometer trials including (1) cardiopulmonary exercise tests (CPET) with face covering, and (2) CPET without face covering. Cognitive testing will occur incrementally as exertion increases.

SPECIFIC AIMS & OUTCOMES

Phase I:

The proposed study consists of 4 specific aims:

Specific Aim 1: Describe the primary and secondary outcomes of athletes during a Cardiopulmonary Exercise Test (CPET) on a treadmill with (arm 1) and without (arm 2) the use of a face covering.

Specific Aim 2: Conduct a randomized crossover trial to determine if there is a significant difference in maximal and submaximal aerobic exercise capacity (VO₂ max; assessed during the CPET) in athletes with (arm 1) and without (arm 2) the use of a face covering.

Specific Aim 3: Describe participants' experiences' while wearing a face covering during exercise.

Specific Aim 4: Determine reliability of the Attitudes Toward Face Coverings Questionnaire

Primary Outcomes:

- VO₂ max during treadmill Cardiopulmonary Exercise Testing (CPET)
- Test duration (time) on a CPET

Secondary Outcomes

- Minute ventilation (VE) at max during CPET

- Subjective dyspnea rating (Borg) at max during CPET
- Subjective exertion rating (Borg) at max during CPET
- O₂ saturation at baseline, each stage, and recovery during CPET
- Blood pressure at baseline, each stage, and recovery during CPET
- Max heart rate during CPET
- Respiratory quotient at max during CPET
- Attitudes Toward Face Coverings Questionnaire
- Scale of Measuring Subjective Perceptions Questionnaire

Phase II:

Specific Aim 1: Describe the primary and secondary outcomes of participants during a Cardiopulmonary Exercise Test (CPET) on a cycle ergometer with (arm 1) and without (arm 2) the use of a face covering.

Specific Aim 2: Conduct a randomized crossover trial to determine if there is a significant differences in cognitive performance outcomes in participants with (arm 1) and without (arm 2) the use of a face covering. Cognitive performance will be measured by simple reaction time and accuracy on the SRT task.

Specific Aim 3: Describe differences in outcomes between participants with and without previous history of COVID-19 diagnosis

Primary Outcomes:

- VO₂ max during CPET
- Test duration (time) on a CPET
- Reaction time (measured in milliseconds) and percentage accuracy on the SRT task

Secondary Outcomes:

- Minute ventilation (VE) at max during CPET
- Subjective dyspnea rating (Borg) during CPET
- Subjective exertion rating (Borg) during CPET
- O₂ saturation at baseline, each stage, and recovery during CPET
- Blood pressure at baseline, each stage, and recovery during CPET
- Max heart rate during CPET
- Respiratory quotient at max during CPET
- Blood lactate during CPET

[figure not shown]
INVESTIGATIONAL PLAN

Research Design and Methodology

Phase I:

In this prospective, randomized crossover trial of eligible athletes, we will compare VO₂ max during two maximal cardiopulmonary stress exercise tests (CPET), seven to ten days apart. Subjects will be randomized into either the face covering or non-face covering group using a 1:1 randomization scheme, stratified by sex, and will serve as their own control in the subsequent test seven to ten days later (see Figure 1. Randomization diagram, below). A within-subjects analysis will be performed stratified by sex.

[figure not shown]
Figure 1. Phase I Randomization diagram

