Participant characteristics will be summarized with means and standard deviations or medians and interquartile ranges for numerical variables, and counts and percentages for categorical variables. The primary outcomes, VO₂ max and test duration, will first be assessed for normality using a Kolmogorov-Smirnov test prior to determining the analysis to be used. If the distribution meets the normality assumption, paired t-tests will be used to determine if there is a difference between participants when wearing and not wearing a face covering. If the distribution does not meet the normality assumption, Wilcoxon signed-rank tests will be used. All secondary outcomes will follow the same analysis plan of assessing the normal distribution assumption to determine the appropriate test for each outcome. Inter-rater reliability analysis will be conducted for the Attitudes for Face Coverings Questionnaire. All analysis will be performed using SAS 9.4 at a 0.05 significance level.

Risks & Benefits

- Physical risks: The potential risks include any and all risks associated with exercise including muscular injury, increased blood pressure and heart rate, and cardiac arrest. Other risks include hypoglycemia post-exercise and lightheadedness or syncope. Although some risks are unavoidable, the careful monitoring of signs and symptoms by the subject and clinical staff will minimize these risks.
- No psychological risks have been identified by participating in this study.
- No social risks have been identified by participating in this study.
- No economic risks have been identified by participating in this study.
- No legal risks have been identified by participating in this study.
- Potential benefits: Participants in this study may experience greater confidence in performing aerobic activities and may gain a better understanding of their personal functional exercise capacity at the time of testing. Participants may also better understand their body's response to exercise with and without a face covering which may impact training and performance in recreational and occupational ventures.

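### Phase I Aim 2 promises a test of submaximal as well as maximal aerobic capacity, but no listed outcome or analysis covers the submaximal part

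*Combined protocol and SAP*

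**What the plan says.** In Specific Aims & Outcomes, Phase I Aim 2 is to determine by randomized crossover whether there is a "significant difference in maximal and submaximal aerobic exercise capacity"; the parenthesis that follows names VO2 max and no second measure. Of the four Phase I aims it is the only one that tests a hypothesis about the exercise test: Aims 1 and 3 are descriptive, and Aim 4 concerns questionnaire reliability.

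The primary outcomes are "VO₂ max during treadmill Cardiopulmonary Exercise Testing (CPET" (closing bracket omitted) and "Test duration (time) on a CPET". The secondary outcomes include "Minute ventilation (VE) at max during CPET", "Respiratory quotient at max during CPET" and "Max heart rate during CPET". The two Borg ratings are also taken at maximum. O2 saturation and blood pressure are listed at rest, at every stage and in recovery.

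Research Design and Methodology, Phase I, names VO2 max as the quantity to be compared. Data Analysis says that VO2 max and test duration "will first be assessed for normality using a Kolmogorov-Smirnov test prior to determining the analysis to be used", leading to a paired t-test or a Wilcoxon signed-rank test. Secondary outcomes follow the same route.

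**The concern.** VO2 max is by definition a maximal quantity and cannot stand for submaximal capacity. The outcome list separates time points deliberately: some items are at maximum, others at every stage. The absence of a submaximal metabolic outcome is therefore a feature of the list and not an unstated detail.

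Two things are at stake. First, a stated part of the aim goes unanswered. If a submaximal result is reported anyway, then the variable, the stage and the handling of tests of unequal length will have been chosen after the data were available.

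Second, the maximal outcomes depend on when the test stops. Under Phase I CPET Procedures a participant may end the test by choice or by reporting the top of either Borg scale, and the participant knows whether a covering is being worn. Perception or motivation can therefore move peak values and duration. Values at an early stage with the same workload in both tests depend far less on that decision, so they would complement the maximal comparison.

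**Working it through.** The plan gives no figure to reproduce on this point, and no power calculation bears on it. The check is a classification of the 11 listed Phase I outcomes (2 primary, 9 secondary) by when each is measured:

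| Measured | Outcomes | Count |
|---|---|---|
| At maximum | VO2 max, VE, dyspnea, exertion, heart rate, respiratory quotient | 6 |
| Whole test | Test duration | 1 |
| Rest, each stage, recovery | O2 saturation, blood pressure | 2 |
| Questionnaire | Attitudes toward face coverings, subjective perceptions | 2 |

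Total: 6 + 1 + 2 + 2 = 11.

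1. The three metabolic-cart outcomes (VO2, VE, respiratory quotient) and the single heart-rate outcome all fall in the first row.
2. Test duration is fixed by the end of the test, so it is not a submaximal measure.
3. The two stage-level outcomes include submaximal readings, but of oxygenation and blood pressure, not of aerobic capacity.
4. The number of listed outcomes that measure submaximal aerobic capacity is therefore 0 of 11.

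The other sections do not fill the gap. The Phase I design text compares VO2 max. The Phase I Schedule of Assessments lists the exercise test with dyspnea, exertion, pulse oximetry and blood pressure. Data Analysis adds no endpoint beyond those listed. Nowhere is a ventilatory threshold, a fixed-stage VO2 or VE, or a submaximal heart rate defined.

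On feasibility, Phase I CPET Procedures has heart rate monitored throughout and data taken from the metabolic cart after testing, so stage-level values can probably be derived without new measurements. However, that section gives only the warm-up workload (3 minutes at 1.7 speed and 0% incline). The speed, grade and length of later stages are not stated, so a reader cannot verify that a later stage carries the same workload at both visits.

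**The case against.** The strongest reply is that a single word is out of place. The parenthesis in Aim 2, the design text and Data Analysis all point to VO2 max, so the operative plan is consistent, and no primary estimate or test changes. It is true that the maximal comparison stands. But the word is in the aim, and a report written against that aim would owe a submaximal answer. Deleting the word is an acceptable remedy; leaving it is not.

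A second reply is that VO2 and VE at a fixed workload describe the response to that workload and are not clearly a capacity. This stands, and it governs how the added outcomes should be labelled.

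A reader might go further and infer that the plan compares no submaximal physiology at all. The documents do not support that: O2 saturation and blood pressure are outcomes at each stage, and the paired tests extend to all secondary outcomes. Nor do they support the inference that submaximal metabolic data are recorded and then discarded. They say that cart data will be gathered, and are silent on resolution and on what becomes of the stage data.

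**Conclusion.** The point holds as a mismatch between aim and outcomes: the submaximal part of Phase I Aim 2 has no outcome and no analysis (0 of 11 outcomes). It should be corrected, because it affects the only hypothesis-testing aim on the exercise test and the correction is cheap. It does not undermine the VO2 max or test-duration comparison, and it should not be read as a loss of a particular fraction of the aim, since the documents do not weight the two parts.

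The conclusion rests on taking the outcome list as written and on not counting O2 saturation or blood pressure as measures of aerobic capacity. That the remedy needs no new measurement assumes that the cart and heart-rate records can be broken down by stage, which the documents suggest but do not state.

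**What to change.** Add as Phase I secondary outcomes for Aim 2: VO2, VE and heart rate at one treadmill stage, fixed before the data are examined, identical at both visits and early enough that nearly all participants complete it in both tests. Compare them within person by the same paired analysis as VO2 max. Label them as the submaximal response at a matched workload. Treat other stages common to both tests as descriptive.

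The last stage completed in both tests should not be the main contrast. The shorter test determines it, so it depends on the stopping decision and may be close to maximal in one condition.

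State in the protocol the treadmill stages actually used, so that the workload match can be verified.

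If these outcomes are not added, delete the word submaximal from Aim 2 and draw no submaximal conclusion.

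The cost is wording in the aims, procedures and analysis sections, some extra extraction from existing records, and a few more secondary comparisons, which should be reported as such.

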The CPET will be performed in an area with immediate access to an automated external defibrillator (AED). Resting blood pressure, heart rate, pulse oxygenation and will be measured and recorded. Explanation of the Borg dyspnea and exertion scales will occur by an Exercise Physiologist prior to beginning test. Each subject will be asked to perform the exercise test to the best of their abilities. At the beginning of the test, subjects will be instructed to perform a walking warm up of 3 minutes at 1.7 speed and 0% incline.

- The Borg Rating of Perceived Exertion (6-20) scale will be used during the test to assess subjective exertion
- The Modified Borg Dyspnea Scale (0-10) will be used to assess subjective shortness of breath.
- Intermittent blood pressure measurements and pulse oximeter measurements will be taken by an exercise physiologist and heart rate will be monitored constantly.

Testing will be terminated if any of the following occurs: (a) subject becomes symptomatic; (b) pain is reported; (c) subject wishes to terminate test; (d) unsafe drop in blood pressure or hypertension over 250/120 mmHg reported; or (e) subject reports a “20” on Borg RPE scale or “10” on Dyspnea scale. Other termination of the test is reserved for the clinical judgment of research staff to ensure safety of the subject. After termination

of the test, subject will be instructed to perform a walking cool-down of 3 to 5 minutes. After subject has completed cool-down, recovery blood pressure, heart rate and pulse oxygenation will be measured and recorded. After completion of the first test, subject will be scheduled for second CPET 7-10 days later to allow for adequate recovery. When data collection is complete, CPET data will be gathered from metabolic cart and matched with subject testing materials.

Phase II CPET Procedures:

Among individuals with history of COVID-19, an ECG will be performed prior to CPET procedures and will be monitored throughout the CPET.

The CPET will be performed in an area with immediate access to an automated external defibrillator (AED). Resting ECG (among individuals with history of COVID-19), blood pressure, heart rate, pulse oxygenation, and blood lactate will be measured and recorded. Explanation of the Borg dyspnea and exertion scales will occur by an Exercise Physiologist prior to beginning test. Each subject will be asked to perform the exercise test to the best of their abilities.

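### Late-stage paired comparisons of O₂ saturation and blood pressure use only participants who reached that stage in both tests: few pairs, selected by stopping time, and open to bias if stopping is linked to the mask effect

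*Combined protocol and SAP*

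**What the plan says.** Under Specific Aims & Outcomes, the secondary outcomes of both phases include "O₂ saturation at baseline, each stage, and recovery during CPET" and "Blood pressure at baseline, each stage, and recovery during CPET". The primary outcomes of both phases include "Test duration (time) on a CPET".

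Data Analysis states the tests for the primary outcomes. Under normality, "paired t-tests will be used to determine if there is a difference between participants when wearing and not wearing a face covering". Otherwise, "If the distribution does not meet the normality assumption, Wilcoxon signed-rank tests will be used". It then extends this: "All secondary outcomes will follow the same analysis plan of assessing the normal distribution assumption to determine the appropriate test for each outcome". The significance level is 0.05.

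On stopping, the CPET procedures of both phases say: "Testing will be terminated if any of the following occurs: (a) subject becomes symptomatic; (b) pain is reported; (c) subject wishes to terminate test". They add a blood-pressure limit, a maximal Borg exertion or dyspnea rating, and staff judgement. In Phase II the workload increments also end when the participant can no longer hold 50 rpm.

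For Phase II, Research Design and Methodology schedules the reaction-time task at the end of every stage, and reaction time and accuracy are listed as a primary outcome.

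The document gives no rule for a stage reached in only one of a participant's two tests. It has no common-stage comparison, repeated-measures model or missing-data method.

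**The concern.** Both named tests need a value from each condition. Once a participant stops, that test yields no later-stage value, and the participant leaves the comparison at every later stage. Each stage is therefore tested on a different set of people, and the set at high workload is the smallest and most selected. The selecting variable, time to stopping, is one that the trial itself treats as possibly affected by the mask. Random allocation of test order does not protect a comparison restricted in this way.

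At stake is the reading at hard exertion, which is where the trial's interest lies. A small or null late-stage difference from a handful of selected pairs could be taken as evidence that a face covering does not lower saturation near maximum. Under other conditions the same selection could exaggerate a difference. For blood pressure, stopping depends directly on the outcome, because exceeding the blood-pressure limit ends the test. In Phase II the same gap reaches a primary outcome.

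**Working it through.** The documents give no stage count, effect size, SD or expected number of pairs, so there is no stated figure to reproduce. The only inputs from the documents are 50 participants per phase, the paired tests and the 0.05 level (taken as two-sided). Everything else below is assumed, to show size and direction.

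**Illustration A (in stages).** Assumptions: unmasked test lasts U = 5.5 (SD 1) stages; the mask shortens it by S = 0.5 (SD 0.5) stage, so the masked test lasts M = U - S; the personal mask effect on O₂ saturation is -1.0 point (SD 1.5), the same at every stage; ρ is the correlation between a larger personal desaturation and greater shortening. A pair exists at stage k only if U ≥ k and M ≥ k. The estimate is the mean personal effect among those pairs, by simulation.

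| Stage | Pairs of 50 | ρ = -0.3 | ρ = 0 | ρ = 0.3 | ρ = 0.5 | ρ = 0.7 |
|---|---|---|---|---|---|---|
| 5 | about 24 | -1.14 | -1.00 | -0.86 | -0.76 | -0.67 |
| 6 | about 8.5 | -1.24 | -1.00 | -0.76 | -0.61 | -0.44 |

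About 48 pairs remain at stage 3 and 40 to 41 at stage 4.

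**Where the pairs go.**
- Stage 5: 50 × Φ((5 - 5.5)/1) = 50 × 0.309 = 15.4 participants do not reach it even unmasked. About 50 - 24.4 = 25.6 pairs are lost, so 15.4/25.6 = 60% of the loss is of this kind and about 10 pairs are lost because only the masked test stopped short.
- Stage 6: 50 × Φ((6 - 5.5)/1) = 50 × 0.691 = 34.6 of 50 - 8.5 = 41.5 lost pairs, or 83%.

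**Illustration B (in minutes, different assumptions).** Unmasked duration 15 (SD 2.5) min, shortening 1 (SD 1.5) min, effect -1.0 (SD 1.0). Pairs available at 9, 12, 15 and 18 min: 96%, 74%, 33% and 6%, against 99%, 88%, 50% and 12% still running unmasked. The estimate at 15 min is -0.75 (ρ = 0.6), -0.88 (0.3), -1.00 (0) and -1.12 (-0.3). With 2 min of shortening these become -0.64, -0.82, -1.00 and -1.18. At 9 min the bias is at most 0.05 in every scenario tried.

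**Precision.** For a two-sided paired t-test (noncentral t), the standardised effect detectable with 80% power is 0.40 with 50 pairs, 0.58 with 25, 0.78 with 15 and 1.00 with 10. At an effect of 0.40, power falls from 79% (50 pairs) to 48% (25) and 30% (15). This loss occurs whatever ρ is.

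**The alternative.** On Illustration A, comparing at the highest stage completed in both tests keeps 49.99 of 50 participants and returns -1.00 at every ρ, given a constant effect. If the personal effect instead grows in proportion to stage and averages -1.00 at stage 5, the same comparison gives about -0.93 (ρ = -0.3) to -0.80 (ρ = 0.7), because many participants are compared below stage 5.

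**The case against.** A reader might infer that late-stage results must understate the mask effect. The documents do not support that. Nothing in them links early stopping to desaturation or to a blood-pressure change, or states which direction is expected. The working shows no bias when the link is absent and overstatement when it is reversed. A link toward understatement is plausible, since symptoms and maximal dyspnea end the test, but it is not established.

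A reader might also infer that the missing pairs are people whom the mask stopped. On the assumed values, most of them would not have reached the stage unmasked, and any maximal test loses them. A pair is also lost when the unmasked test is the shorter one.

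It can further be said that Data Analysis never explicitly prescribes a separate test at each stage, and that Aim 1 of each phase is descriptive. This is fair: stage-wise testing is an inference from outcomes defined at each stage and a test chosen for each outcome. It is the natural reading, and no other is offered.

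Finally, every magnitude is assumed, and the Phase I procedures define no treadmill stages. The stage-5 bias in Illustration A (0.14 to 0.33 points for ρ of 0.3 to 0.7) is about one standard error or less (1.5/√24 = 0.31). Any measurement noise within the assumed SD would weaken the link and the bias. These points limit the size and certainty of the problem. They do not supply the missing rule or change who can be paired.

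**Conclusion.** The point holds in conditional form. As written, late-stage paired comparisons of O₂ saturation and blood pressure rest on few pairs, selected after randomisation by stopping time. The consequence depends on an unknown link: bias toward no effect if those the mask stops earlier have the larger physiological change, bias away from it under the opposite link, and lost precision alone if there is none. The sizes in the working illustrate this on assumed inputs and do not predict this trial's results; none was worked out for blood pressure.

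The reach is limited. Baseline, recovery and the outcomes taken at maximum do not lose pairs this way, early stages lose few, and the analyses of VO₂ max and test duration are untouched. Phase II reaction time and accuracy are exposed for the same reason, with more consequence because they are a primary outcome. The matter should be settled before analysis, because following the plan as written can mislead at the workloads of most interest and the remedy is cheap.

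**What to change.** In Data Analysis:

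- Make the inferential within-exercise comparison of O₂ saturation and blood pressure the value at the highest stage the same participant completed in both tests, with one value per condition entering the paired test. State how a stage is defined for this purpose in each phase.
- Report stage-by-stage values descriptively only, with the number of pairs and the number stopped by condition at each stage.
- Leave the baseline and recovery comparisons as they are.
- Apply the same rule to Phase II end-of-stage reaction time and accuracy. Data Analysis names only VO₂ max and test duration as primary outcomes, so this also fills a gap there.

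The cost is a few sentences and a little programming on measurements already planned. The downside should be stated in the plan: the common stage differs between participants and is partly set by the mask. If the mask effect grows with workload, the result averages over lower workloads and is not the effect at peak exertion.
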